- Rate of recanalization by clot density on CT (hyperdense vs isodense). There is evidence that hyperdense clot contains a higher fraction of red blood cells, is softer, and is more readily removed with thrombectomy devices. This has not been assessed in aspiration thrombectomy.

Risk Assessment

- This study poses no more than minimal risk to participants. All subjects will undergo a standard mechanical thrombectomy procedure, with the only difference being the method of aspiration; either static or cyclic (Plunger) technique. Both techniques are widely used in clinical practice, are considered standard of care, and have comparable safety profiles. No investigational devices or procedures will be used. As such, participation in the study does not expose subjects to risks beyond those encountered in routine clinical care.

Investigational plan

Trial design

The Plunger trial is a prospective, multicenter, randomized, controlled trial of the Plunger technique vs. static manual direct aspiration thrombectomy to assess recanalization efficacy for treatment of acute large vessel occlusion stroke. Participants will have a large vessel occlusion in the anterior circulation of the terminal ICA or M1 segment of the MCA.

Ethical Considerations and Informed consent

This study compares two suction techniques: static aspiration and the cyclic aspiration (plunger technique) both of which are standard practices in mechanical thrombectomy. These techniques are routinely employed by physicians based on individual preference and training. All procedures involved are part of routine clinical care and utilize FDA-cleared devices (e.g., Raptor catheters and 60cc VacLok syringes). No investigational devices or experimental procedures are introduced. Importantly, both techniques have similar/identical risk profiles, as they are commonly used in clinical practice and do not introduce additional risks beyond those encountered in standard stroke treatment. Therefore, this study meets the definition of minimal risk research under federal regulations.

Informed consent process:

The patient consent process will be conducted using a REDCap-based electronic consent form. The consent form has been developed in REDCap, a secure, web-based, HIPAA-compliant, data collection platform with a user management system allowing project owners to grant and control varying levels of access to data collection instruments and data (e.g. read only, de-identified-only data views) for other users.

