Patients with a large vessel occlusion who are clinically appropriate for thrombectomy will be screened for participation. Subjects who meet selection criteria below will be enrolled. Note that there are no parenchymal imaging criteria; site investigators will determine if individual patients will benefit from thrombectomy. The trial is not intended to assess clinical criteria for endovascular treatment decisions, but rather to assess *technique* of thrombectomy once that decision has been made.

Inclusion criteria

1. Acute ischemic stroke due to occlusion of the terminal ICA or M1 segment of the MCA
2. Treatment can be initiated within 24 hours of onset
3. Age of 18 years or older

Exclusion criteria

Evidence of acute intracranial hemorrhage prior to treatment

Failure to obtain informed consent

Subject withdrawal

Subjects enrolled in the study can discontinue their participation at any time for any reason without prejudice or reduction in the quality of their medical care. The investigator can terminate a subject's participation in the study to protect the subject's health. The Investigator must document this notification of withdrawal from the study in the appropriate CRF and notify the sponsor.

Data collection

Baseline data: At the time of endovascular treatment, the following data will be collected for all subjects:

- Age
- Baseline mRS
- ASPECTS score
- Hyperdense vessel sign (yes/no; site-reported)
- NIHSS
- Location of occlusion (right or left, ICA terminus or M1)

Procedure data: The following will be collected immediately after the procedure:

- Guide catheter used
- Which Raptor used (0.071" or 0.074")
- Microcatheter used (Carrier or other)
- Microwire used
- Successful navigation? (yes/no)

- Total duration of aspiration
- Total duration of plunging (if assigned to Plunger technique)
- Reperfusion (TICI) after each pass (site-assessed)
- Clot ingestion: none, partial, or complete
- Groin puncture time
- On-clot time
- Time of reperfusion
- Rescue treatment? If yes, what device and how many passes

24 hour data: To be collected at 24 hrs post-procedure +/- 6 hours:

- Imaging evidence of hemorrhage? If parenchymal, HI1, HI2, PH1, or PH2; or IVH, SAH, SDH
- Symptomatic ICH?
- NIHSS

90 day follow up: To be collected by phone at 90 days +/- 30 days

- Modified Rankin Score

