- PROMIS-10 score (a publically available global health assessment tool that allows measurements of symptoms, functioning, and healthcare-related quality of life for a wide variety of chronic diseases and conditions.

Telephone follow up

Telephone follow-up will be conducted where information related to the subject's mRS assessment and Quality of Life assessment will be collected. If the subject is unavailable for any reason, the subject's family/relative or caregiver/LAR will be requested to provide the applicable information.

Schedule of assessments

	Baseline	Procedure	24 hours Post Procedure	90 days Post Procedure (telephone)
Eligibility	♦			
Demographics and Medical History	♦			
Location of occlusion	♦			
mRS Assessment	♦			♦
NIHSS Assessment	♦		♦	

Head CT: ASPECTS, hyperdense vessel, hemorrhage	♦		♦	
Devices used		♦		
Successful navigation		♦		
Time of aspiration, plunging, and time to reperfusion		♦		
Reperfusion score (TICI; site-assessed and core lab)		♦		
Rescue treatment, if applicable		♦		
Clot ingestion		♦		
PROMIS-10				♦
Adverse Events		♦	♦	♦

Recording data

Study data will be collected using electronic case report forms and a electronic data capture system (REDCap). The system allows the capability of data collection remotely through the internet so the participating clinical site personnel may log on to the system securely and enter the data. All subjects' data collected in the system will be extensively verified through data validation programs, database integrity rules, and investigation-specific data entry conventions for data accuracy and logical meaningfulness. Periodic analysis of all subjects' data collected will be performed in order to examine the expected distributions of data and to identify outliers for possible data entry errors.

The Investigator is responsible for reviewing all eCRF entries for completion and correctness. Changes in case report forms will be made electronically and the system used will keep an audit trail of changes. If necessary, an explanation for the change(s) may be provided. The Investigator will electronically approve all eCRF data.

All study staff that enter data into eCRFs will undergo appropriate training for use of eCRFs.

Loss to Follow-up

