A participant will be considered lost to follow-up for the secondary end-point, mRS, if he or she is unable to be contacted by the study site staff, either via telephone or an in-person meeting at 90-days after randomization. When all reasonable attempts to locate the subject have been exhausted, the subject will be considered lost to follow-up and their data will be excluded from the data analysis from the time of last contact onward. All data collected prior to last contact will be included in data analysis.

Statistical analysis

Sample size calculation

The true rate of successful FPE with aspiration thrombectomy can be estimated based on several prior studies. The COMPASS trial reported an 83% rate of TICI 2b or 3 after the first attempt with aspiration thrombectomy [4]. Similarly, Kang et al reported TICI 2b or 3 in 82% of patients after the first pass with aspiration thrombectomy [8], but that rate dropped to 19% when limiting the definition of successful FPE to TICI 2c or 3 [8]. Similarly, the ETIS investigators reported a 24% rate of TICI 3 FPE with the Sofia catheter [9]. Synthesizing these results, we estimate the predicted FPE (TICI 2c or 3) rate of static aspiration thrombectomy to be 25%.

While it is difficult to predict the treatment effect of the Plunger technique, our experience is that there is significantly more total clot ingestion with this technique. Total clot ingestion would be expected to particularly impact the TICI 2c/3 rate of FPE. Therefore, we estimate that the Plunger technique may increase FPE rate by 15% over static aspiration (predicted Plunger FPE of 40%).

A minimum sample size of 462 would be required to detect a difference of 15% between these two groups with 90% power at alpha of 0.05. Given that the actual FPE rates are difficult to estimate and accounting for inability to access the lesion with the Raptor and missing data, we plan for a total minimum sample size of 500.

Population for analysis

A modified intention-to-treat (mITT) analysis will be employed, wherein all subjects for whom navigation of the Raptor to the clot failed will be excluded from the subsequent ITT analyses. This is because those subjects will not be treated by either of the techniques being studied in this trial. Once navigation failures are excluded, the remainder of the population will be compared based on assigned treatment technique per randomization.

Analysis of primary effectiveness endpoint

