- a. A board-certified radiologist will interpret all images as required by the protocol. All reads will be interpreted in a blinded fashion. [name] would be the primary reader unless the sponsor requests a different physician.
- b. Summary images and image interpretations will be uploaded to the study-specific server site. All reads will be immediately available to the sponsors. Images and any interpretation data can be reviewed by site users as required by the protocol.
- c. The core lab will select images of interest during review. These will be immediately available for review by the sponsor or sponsor's designee from any web enabled device.
- d. The sponsor or any sponsor designee will have access to the entire imaging dataset once it has been validated for HIPAA compliance via download from our server. Our standard imaging turn-around time is 14 days from submission.

6. Imaging Data Reporting

- a. All imaging data collected during the trial will be saved on our secure database.
- b. Images and draft imaging reports are available via secure web access.
- c. These may be downloaded in PDF or excel format. These may also be downloaded in csv format to allow importing into other EDC systems.

Study Management and Oversight

Vanderbilt University Medical Center (VUMC) will serve as the coordinating center for this study. The VUMC team will be responsible for:

- Study protocol development and amendments
- Informed consent templates and revisions
- IRB approvals and correspondence
- Site initiation and training materials
- Case Report Forms (CRFs) and data collection tools
- Monitoring reports and audit documentation
- Adverse event and protocol deviation reporting
- Regulatory compliance (e.g., certifications, CVs, signature pages)
- Communication logs with participating sites
- Final study report and data safety monitoring documentation

Institutional review boards

The site investigator must submit this clinical protocol and subject informed consent form to the appropriate IRB. The study will not start at a clinical site and subjects will not be enrolled until a copy of written and dated approval/favorable opinion has been issued by the site.

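### The protocol masks the core-lab angiogram reads but not the 90-day telephone mRS, so a site may follow the plan and have someone who knows the arm grade the only listed functional endpoint

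*Protocol*

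**What the plan says.** Trial design describes a "prospective, multicenter, randomized, controlled trial of the Plunger technique vs. static manual direct aspiration thrombectomy" and uses no masking term for the trial as a whole.

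The 90-day mRS is the only functional outcome under Secondary endpoints. Data collection lists it together with PROMIS-10: "To be collected by phone at 90 days +/- 30 days". Telephone follow up repeats that the "mRS assessment and Quality of Life assessment will be collected" by telephone. If the subject is unavailable, "the subject's family/relative or caregiver/LAR will be requested to provide the applicable information". That section does not say who calls. The caller is identified only indirectly, under Loss to Follow-up, where a participant counts as lost if "unable to be contacted by the study site staff, either via telephone or an in-person meeting at 90-days after randomization".

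Analysis of secondary endpoints compares mRS and PROMIS-10 between arms by ordinal shift analysis.

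Masking appears in one place, the Angiographic core lab section, which has each angiogram assessed blind and adds: "All reads will be interpreted in a blinded fashion". No section masks the 90-day caller, the mRS rater, the subject or the proxy, and none names an independent or central assessor.

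**The concern.** The operator carries out the assigned technique and so knows the arm. The arm can also be read from the site's record, because the procedure data include a plunging duration that applies to one arm only. With the 90-day contact left to site staff and no restriction on who calls, the treating team may grade the outcome.

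The mRS call needs judgement between adjacent grades, sometimes through a proxy. An ordinal shift analysis uses every grade boundary, so a tendency to settle borderline cases one grade better in one arm enters the estimate directly. The Background gives some reason to take this seriously. It says that the technique was developed by the study's own group, that three of four attendings at the coordinating center prefer it, and that individual operators have firm habits in either direction.

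At stake is whether a 90-day functional result, positive or null, can be taken at face value. Who makes the call is trial conduct, and a later SAP cannot mask a call already made.

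**Working it through.** The plan gives no figure on this point to reproduce. The check is therefore a reading of the sections, followed by an illustration of size.

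**1. Sections side by side**

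| Outcome | Who assesses | Masking stated |
|---|---|---|
| First pass effect (primary) | Core lab | Yes |
| 90-day mRS (secondary) | Site staff, by telephone; subject or proxy answers | No |
| 90-day PROMIS-10 (collected and analysed; not in the endpoint list) | Self- or proxy-rated in the same call | No |

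**2. Inputs for the illustration**

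- From the protocol: total N 500 and 1:1 allocation, hence 250 per arm; comparison by ordinal shift.
- Assumed, not in the documents: an mRS 0-6 distribution of 10/17/19/16/14/6/18% in both arms (no true effect); two-sided alpha 0.05 for this comparison; no loss to follow-up and no navigation exclusions.
- Assumed misgrading: in one arm, a share f of subjects at each of mRS 1 to 5 is recorded one grade better. Scores 0 and 6 are left alone.

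**3. How many subjects that is**

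The mRS 1-5 share is 17 + 19 + 16 + 14 + 6 = 72%, or 0.72 × 250 = 180 subjects in the arm. So f = 5%, 10% and 20% means 9, 18 and 36 misgraded subjects.

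**4. Shifted distribution, for example at f = 10%**

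- mRS 0: 10 + 1.7 = 11.7%
- mRS 1: 17 − 1.7 + 1.9 = 17.2%
- mRS 2: 19 − 1.9 + 1.6 = 18.7%
- mRS 3: 16 − 1.6 + 1.4 = 15.8%
- mRS 4: 14 − 1.4 + 0.6 = 13.2%
- mRS 5: 6 − 0.6 = 5.4%
- mRS 6: 18%

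The sum is 100%. The share with mRS 0-2 moves from 46.0% to 47.6%.

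**5. Effect on the test**

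A proportional-odds model fitted to the expected counts gives a log odds ratio b with standard error 0.157. With z = b / 0.157, the rejection rate is Φ(z − 1.96) + Φ(−z − 1.96).

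| f | b | Spurious common OR | z | False-positive rate |
|---|---|---|---|---|
| 5% | 0.035 | 1.04 | 0.22 | 5.6% |
| 10% | 0.069 | 1.07 | 0.44 | 7.2% |
| 20% | 0.138 | 1.15 | 0.88 | 14.2% |

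**6. Sensitivity to the assumptions**

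A second assumed distribution (10/17/15/15/15/8/20%), analysed with a tie-corrected Wilcoxon-type test at 250 per arm, gives odds ratios of about 1.04, 1.07 and 1.14. The false-positive rates are 5.5%, 6.8% and 12.4%. The two sets agree closely at 5% and 10% and span about 12-14% at 20%.

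**The case against.** The strongest reply is that much here is silence. The protocol never calls itself open-label and never says that the caller is unmasked. A reader might infer both, but the text supports only that masking of the 90-day assessor is not stated.

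A reader might also infer that the staff who randomize and enter the procedure data are those who telephone at 90 days. The Randomization and Data collection sections name no actor, so this is permitted, not stated. Nor do the documents give a reason for masking the core lab, so it cannot be said that the sponsor recognised this risk for TICI and overlooked it for the mRS.

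The preference evidence is limited too. It concerns operators, not callers. The figures come from the coordinating center, and the individual examples point in both directions, whereas the illustration moves every misgrade the same way. The misgrading rates are assumed, and at 5-10% the distortion is small.

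Finally, the argument about grading does not carry over to PROMIS-10, which the subject or proxy rates. There the question is what the respondent knows and how the interviewer might influence the answers. The protocol does not say whether participants or relatives are told the technique.

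These points limit the claim. They do not remove the gap: the protocol specifies masking for one outcome and leaves the other open, and a site could comply fully with an unmasked grader.

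**Conclusion.** The point stands as a gap in trial conduct that should be closed. As written, the 90-day mRS may be graded by a member of the treating team, and its ordinal comparison is open to assessor bias.

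The size is modest unless misgrading is common. The false-positive rate is about 5.6% at 5% misgrading, about 7% at 10%, and 12-14% at 20%, with spurious odds ratios of about 1.04, 1.07 and 1.15. These figures rest on assumed mRS distributions, one-directional misgrading, 250 analysed per arm and no true effect. They show scale and do not predict what will happen.

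A reader might go further and conclude that the trial's main result is compromised. It is not: first pass effect is read blind by the core lab, and this point concerns secondary outcomes only.

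**What to change.** In Secondary endpoints and Telephone follow up, state that:

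- the 90-day mRS is taken by an existing, trained site team member who was not at the procedure and whose REDCap role hides the randomization and procedure forms;
- the caller uses a structured mRS script, asks the respondent not to disclose the technique, and records whether masking held;
- the mRS is scored and locked before any 90-day adverse event relatedness assessment, since adverse events are also scheduled at that contact and their relationship to technique must be evaluated;
- the investigator's approval of eCRF data does not alter the masked score.

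For PROMIS-10, the same caller and script limit interviewer influence. The protocol should also state whether participants and relatives are told the technique before the call. If the answer is to withhold it, the consent material must agree.

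The cost is small. The Informed consent process section already describes REDCap as "allowing project owners to grant and control varying levels of access to data collection instruments and data", so hiding the forms is a matter of user roles, plus a script and brief training. The downside is that each site must assign the call to someone not involved in the case. The protocol gives no site staffing, so that such a person is available is an assumption to confirm with sites. Endpoints, sample size and care do not change, but the arrangement must be in place before the 90-day calls are made.

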The primary endpoint is the first pass effect (FPE), defined as TICI 2c or 3 after the first attempt of direct aspiration thrombectomy, as determined by core lab assessment. The rate of successful FPE will be compared between the Plunger group and the static aspiration group per the mITT population as above.

Null hypothesis: the rate of successful FPE is not different between static and plunger aspiration. The rate of FPE will be compared between the two groups by chi-square analysis. If there is a significant difference between the two, then the null hypothesis will be rejected.

Analysis of primary safety endpoint

The primary safety endpoint is the rate of sICH at 24 hours compared between the static and Plunger aspiration groups. A chi-square test will assess for differences in rate of sICH between the two treatment groups in the mITT population. Secondary analyses will account for ASPECTs score and time to treatment between the two groups.

Analysis of secondary endpoints

Overall rate of TICI 2b or 3 recanalization with Plunger vs. static aspiration will also be compared using chi-square analysis on the mITT population.

For the following additional binomial secondary efficacy endpoints, treatment groups will be compared using logistic regression models as appropriate:

- Rate of successful navigation of aspiration catheter to clot
- Rate of rescue treatment with stent-retrievers
- Rate of complete clot ingestion
- Rate of recanalization by clot density on CT (hyperdense vs isodense)

The 90-day functional outcomes, including mRS and PROMIS-10, will be compared between the two groups using ordinal shift analysis.

Randomization

Patients will be randomized (1:1; permuted block randomization) once the decision is made for patient to go for thrombectomy using the REDCap randomization tool.

Adverse events

Throughout the course of the clinical investigation, all adverse events will be recorded on the applicable Adverse Event CRF. The date of onset, date of resolution, severity, and action taken will be evaluated by the Investigator. The relationship to the technique or device, relationship to the procedure, and clinical significance will be evaluated. The neurological outcomes and adverse events will be reported.

Adverse Event Classification and Definitions

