The Investigator is required to report all SAEs within 72 hours after first learning of the event. The primary method of reporting SAEs will be through the eCRFs. All SAEs will also be reported to the local IRB.

Site selection

Potential clinical sites will be assessed to ensure the investigator and his/her staff have the facilities, expertise required for the study and ability to conduct the study according to the clinical protocol.

To participate in this trial a clinical site must have, at a minimum, the following:

- 24/7 stroke interventional capabilities
- CT-based acute stroke imaging protocols (MRI is not acceptable)
- Ability to support timely data collection via an Internet-based EDC system
- Resources for conducting the informed consent process
- Willingness to adhere to the study protocol

Angiographic core lab

The procedural angiograms will be submitted by each site with all subject identifiers removed and only the assigned subject study number on the images. Each angiogram will be blindly assessed by the core lab for:

- Reperfusion score after first pass
- Reperfusion after final aspiration pass
- Reperfusion at end of procedure

Oculus Imaging, LLC, will serve as the core lab. The core lab services will include:

1. Trial Specific Website Design

- a. We will customize a user accessible website on our server specifically for the requested study. All imaging aspects of the study will be managed through this site.
- b. The primary functions of the site include electronic image submission, de-identification, and analysis.
- c. The website may also allow users or sponsors to review subject images and the dynamic trial reports as needed.
- d. Our study websites are secure, HIPAA, FDA, (CFR part 11) and E-Union compliant. Daily backups are performed.
- e. Studies are stored in at least two separate off-site archive sites.
- f. After launch of the trial website, any requested changes to the data collection for this trial may require a database change. Such requests would be reflected in a new version of the trial guidelines. Database changes may require revalidation of the trial imaging reports and additional fees may apply.

2. Imaging Protocol

- a. Oculus Imaging will write the Imaging Guidelines detailing imaging modalities to be used, imaging acquisition protocols, and procedures for image transfer.

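### The protocol's exclusion rule makes the 90-day mRS comparison an unadjusted available-case analysis, although recorded predictors would support a weaker missing-data assumption (minor; secondary endpoint only)

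*Protocol*

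**What the plan says.** The Loss to Follow-up section defines loss specifically for the mRS endpoint. Once a participant is declared lost, "their data will be excluded from the data analysis from the time of last contact onward"; data obtained before that point are kept.

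Data collection sets the follow-up mRS as "To be collected by phone at 90 days +/- 30 days". The Schedule of assessments shows mRS at baseline and at the 90-day call, with nothing in between.

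Analysis of secondary endpoints states: "The 90-day functional outcomes, including mRS and PROMIS-10, will be compared between the two groups using ordinal shift analysis". It names no covariates and no method for missing values.

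Data collection also lists age, baseline mRS, NIHSS at baseline and NIHSS at 24 hours. The Angiographic core lab section adds a blinded reading of reperfusion at the end of the procedure. All of these are obtained well before the 90-day call.

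**The concern.** With a single post-baseline mRS, excluding a lost participant from last contact onward removes that person from the 90-day comparison altogether. The ordinal analysis then uses only those who were reached. That gives the right mRS distribution in each arm if, within the arm, being reached has nothing to do with outcome. In stroke follow-up this is a strong assumption, since disability may well affect who can be reached.

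The trial holds the information needed to relax it. The 24-hour NIHSS and final reperfusion are likely to be informative about 90-day function, but they are measured after randomization and may be affected by the technique. They therefore do not belong as covariates in the main treatment comparison. An imputation model can use them without changing the treatment effect being estimated; the exclusion rule leaves them unused.

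At stake is how far the absolute 90-day outcome in each arm can be trusted and, if loss differed by technique, the between-arm comparison of a secondary endpoint.

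**Working it through.** **1. What the protocol gives.** There is no loss rate, mRS distribution, mRS effect size or mRS power figure to reproduce. Sample size calculation says that the total of 500 allows for missing data, without a rate. The numbers below are therefore an illustration with assumed inputs.

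**2. Effect within an arm.** Let p be the true share with mRS 0–2, Lg the loss among them, and Lp the loss among the rest. The available-case share is

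p(1 − Lg) / [p(1 − Lg) + (1 − p)(1 − Lp)].

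Assume p = 0.45 and Lg = 0.05, so p(1 − Lg) = 0.4275.

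| Lp | (1 − p)(1 − Lp) | Overall loss | Share as read | Shift |
|---|---|---|---|---|
| 5% | 0.5225 | 5.0% | 0.4275/0.9500 = 45.0% | 0 |
| 10% | 0.4950 | 7.8% | 0.4275/0.9225 = 46.3% | 1.3 points |
| 15% | 0.4675 | 10.5% | 0.4275/0.8950 = 47.8% | 2.8 points |
| 20% | 0.4400 | 13.3% | 0.4275/0.8675 = 49.3% | 4.3 points |

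**3. Effect on the comparison.** Available-case selection multiplies the odds of mRS 0–2 in an arm by (1 − Lg)/(1 − Lp).

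- *Same loss pattern in both arms:* the factor cancels, and the odds ratio for mRS 0–2 is unchanged in every row above.
- *Different pattern:* if one arm loses 5% of good and 10% of poor outcomes and the other loses 5% of each, the odds ratio is multiplied by (0.95/0.90)/(0.95/0.95) = 1.056. A true odds ratio of 1.00 would read about 1.06.

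A check of the ordinal analysis itself, with about 6.5% loss driven by 24-hour NIHSS (also an assumption), agrees in size. The common odds ratio was essentially unbiased when loss was alike in both arms, and moved by about 4–5% when the loss mechanism differed by arm.

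**4. Outer bounds.** With a loss fraction d in each arm and nothing assumed about the missing values, each arm's share can move over a range of d, so the risk difference spans 2d. For d = 5%, 10% and 20%, 475, 450 and 400 of 500 remain, and the bounds span 10, 20 and 40 points. These are logical limits, not expected bias.

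**5. What imputation changes.** The assumption moves from loss unrelated to outcome given arm, to loss unrelated to outcome given arm and the recorded predictors. To the extent that the link between loss and outcome runs through those predictors, the shifts in steps 2 and 3 can be corrected. Any part that depends on the unobserved mRS itself remains.

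**The case against.** The case for leaving the rule alone has weight. A participant who is truly lost has no 90-day mRS to exclude, so the sentence largely describes what happens anyway. Imputation models are usually specified in an SAP, which is not shown here and could add imputation or sensitivity analyses. The existence of an alternative does not make the stated rule wrong, and the alternative brings an untestable assumption of its own. Nothing suggests that loss differs by arm.

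Most of this stands, and it is why the point is minor. It does not dispose of the point, because the protocol does not leave the handling open: it prescribes exclusion for this endpoint. The criticism is of a stated choice, not of an omission.

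Two stronger readings are tempting, and the document supports neither.

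- *That proxy-reported scores are thrown away.* Loss to Follow-up declares a participant lost "if he or she is unable to be contacted by the study site staff" and does not mention a proxy. But Telephone follow up says: "If the subject is unavailable for any reason", the subject's "family/relative or caregiver/LAR will be requested to provide the applicable information". The proxy call is thus part of the same 90-day contact, and loss is declared only "When all reasonable attempts to locate the subject have been exhausted". No section tells sites to discard a score obtained by proxy. What remains is a gap in wording.
- *That deaths are counted as lost.* The protocol classes death as a serious adverse event, and "The Investigator is required to report all SAEs within 72 hours after first learning of the event". No section treats a known death as loss to follow-up.

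**Conclusion.** The point holds as a minor weakness of method. The protocol's own exclusion rule turns the 90-day mRS comparison into an unadjusted available-case analysis, while variables that would support a weaker assumption are already collected.

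The size cannot be derived from the document. Under the assumed losses above, the absolute share with mRS 0–2 would be overstated by 0 to 4.3 points within an arm. The between-arm comparison is materially affected only if loss differs by arm, for which the document gives no grounds; the example of such a difference moved the odds ratio by about 6%, and the check of the ordinal analysis gave about 4–5%. The available-case result remains usable, and imputation is the better choice rather than the repair of an invalid test. The primary endpoint (FPE) and the 24-hour sICH endpoint are not touched.

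**What to change.** In Loss to Follow-up, replace the exclusion for the 90-day mRS with multiple imputation, carried out separately by arm, from age, baseline mRS, baseline and 24-hour NIHSS and core-lab reperfusion at the end of the procedure. Keep the available-case analysis as a sensitivity analysis.

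As a clarification of wording only, add that an mRS obtained by proxy under Telephone follow up counts as follow-up.

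The cost is one or two sentences and slightly more analysis work; no new data are needed. The downside is a missing-at-random assumption: imputation will not remove bias from loss that depends on the unobserved mRS itself.
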